4.1.4 Safety Population

The Safety Population will include all patients who received any study drug. Randomized patients who receive an incorrect therapy from that which was intended will be summarized in the group according to the therapy actually received. Patients who are not randomized but who receive study drug will be included in the safety population and summarized according to the therapy actually received. Patients who received more than one study therapy will be summarized in the ocrelizumab group. Patients who received only ocrelizumab placebo but not interferon beta-1a 44 µg SC will be included in the interferon beta-1a 44 µg SC–arm group as a conservative approach.

4.1.5 OLE Intent-to-Treat Population

All patients receiving any study drug during the OLE Phase will be included in the OLE ITT population. Patients will be summarized according to their randomized treatment during the double blind treatment period

4.1.6 OLE Safety Population

Similar to the safety population, all patients receiving any study drug during the OLE Phase will be included in the OLE safety population. Patients will be summarized according to the therapy received during the double blind treatment period, consistent with the safety population.

4.2 ANALYSIS OF STUDY CONDUCT

All data up to the point of the clinical cutoff date for each study will be included to evaluate study conduct. This will include complete data from the 96-week, double-blind, double-dummy treatment period and all available data from the OLE and SFU phases at the time of cutoff for the primary analysis. Data from Study WA21092 that relate to the period after the Study WA21092 clinical cutoff date but before the Study WA21093 clinical cutoff date will not be included in the Study WA21092 database that will be used in the primary analysis.

The following analyses will be performed to evaluate the study conduct:

- Summary of protocol violations
- Summaries of ITT, per-protocol-defined, and safety populations, including numbers of patients in each population, and reasons for exclusion from the per-protocol population
- Summary of patient disposition, including the number of Doses received, the number of patients entering into the SFU phase, and the number of patients entering into the OLE phase
- Summary and Kaplan-Meier plots of the following:
 - Time to discontinuation of study treatment during the 96-week, double-blind, double-dummy treatment period
 - Time to discontinuation from the study (available data from all study phases to be included)

After 96 weeks of double-blind phase, all eligible patients from both treatment groups, including patients from IFN group start receiving ocrelizumab treatment in the open-label extension phase. OLE allows additional data being collected for long-term safety and efficacy assessments. Patients who withdraw from treatment during OLE may start safety follow-up.

Analysis to evaluate study conduct as mentioned above will be repeated for the OLE phase as appropriate.

4.3 ANALYSIS OF TREATMENT GROUP COMPARABILITY

For continuous variables, the mean, median, SD, minimum, and maximum will be calculated. For categorical variables, number and percentage in each category will be displayed. The units/categories to be used are indicated within the brackets and separated by commas.

Except where stated, all assessments of treatment group comparability will utilize the date of the baseline visit (not the date of the screening visit) as the reference point in time.

Summaries will be presented for ITT and safety populations.

4.3.1 Demography

- Age (years): summary statistics calculated will include mean, median, SD, minimum, and maximum, percentage, and number in each category (18–39, ≥ 40 , also age categories < 18 , 18–65, > 65 , used in the Development Safety Update Report [DSUR]) will be displayed (age at randomization will be used)
- Sex: the number and percentage of male and female patients
- Race: the number and percentage of White; Black or African American; Asian (Indian Subcontinent, Other than Indian subcontinent), American Indian or Alaskan native; Native Hawaiian or other Pacific Islander; and Other
- Stratification Factor: (Geographical region) the number and percentage of United States and Rest of World patients
 - Sub-region: the number and percentage of patients from European Union/Switzerland/Norway, Latin America, Non-EU/Israel/Africa, and USA/Canada/Australia
- Ethnicity: the number and percentage of Hispanic or Latino and not Hispanic or Latino
- Weight (kg): summary statistics as described for age
- Body Mass Index (BMI): summary statistics as described for age

4.3.2 Baseline Disease Characteristics

- Stratification Factor (Baseline EDSS): the number and percentage of patients in each EDSS category (< 4.0 , and ≥ 4.0); EDSS mean, median, SD, minimum, and maximum will be summarized. The baseline EDSS is defined as the average EDSS score from the screening and baseline visit EDSS scores (only values recorded up to and including the date of randomization will be used). For the analysis of mean change of EDSS, disability progression, and disability improvement, the exact value of the average EDSS score will be used. However, for the stratification factor, and for the randomization algorithm, the average will be rounded up to the next EDSS score, in order to assign a valid score (e.g., round 3.75 to 4.0, round 5.25 to 5.5). If one of the EDSS scores from the screening or baseline visit is missing, the other will be used for baseline EDSS. If EDSS score is missing at both the screening and baseline visit, the patient should not be randomized. Unless otherwise specified, this definition of baseline EDSS is used throughout.
- Number of relapses in the past year: the number and percentage of patients in each category (0, 1, 2, 3, and ≥ 4); a relapse is considered to happen in the past year if: date of randomization – date of relapse is ≤ 365 days

- Number of relapses in the past 2 years: the number and percentage of patients in each category (0, 1, 2, 3, and ≥ 4); a relapse is considered to happen in the past 2 years if: date of randomization – the date of relapse is $\leq (365 \cdot 2)$ days
- Time since last onset of MS relapse prior to randomization (year): the number and percentage of patients in each category (> 6 months prior to randomization, within the last 6 months from randomization); summary statistics calculated will include mean, median, SD, minimum, and maximum (calculated in years, i.e., divided by 365.25). Time is calculated as: date of randomization – the date of last relapse
- Baseline Functional Systems Scores (FSSs) for each category (pyramidal, cerebellar, brainstem, sensory, bowel and bladder, visual, cerebral [or mental]; rated 0–5 or 0–6 depending on the domain of FSS) and for ambulation (categorical; rated 0–12)
- Baseline MSFCS score, raw results for each component: summary statistics calculated will include mean, median, SD, minimum, and maximum

4.3.3 Multiple Sclerosis Disease History

- Duration since MS symptom onset (years): summary statistics calculated will include mean, median, SD, minimum, and maximum (calculated in years; i.e., divide by 365.25)
- Duration since MS diagnosis (years): summary statistics calculated will include mean, median, SD, minimum, and maximum (calculated in years; i.e., divide by 365.25)
- Duration since MS symptom/diagnosis onset will be calculated up to the randomization date. If the month of symptom/diagnosis onset date is missing, the month of January will be used. If the day of symptom/diagnosis onset date is missing, the first (1st) of the month will be used

4.3.4 Non-MS Disease History

- Did patient have a history of any non-MS diseases?: number and percentage of patients, (yes or no)
- Each non-MS disease: number and percentage of patients with a history of each disease

4.3.5 Prior Treatments for Multiple Sclerosis

- Did patient receive any prior treatment for MS?: number and percentage of patients, (yes or no)
- Did patient receive any prior treatment for MS with any interferon or glatiramer acetate?: number and percentage of patients, (yes or no)
- Each prior treatment for MS: number and percentage of patients receiving each treatment

4.3.6 Baseline Magnetic Resonance Imaging Data

- Number of Gd-enhancing T1 lesions at baseline: the number and percentage of patients in each category (0, 1, 2, 3, and ≥ 4); summary statistics calculated will include mean, median, SD, minimum, and maximum
- Volume of T2 lesions at baseline: summary statistics calculated will include mean, median, SD, minimum, and maximum
- Number of T2 lesions at baseline: summary statistics calculated will include mean, median, SD, minimum, and maximum. Also the number and percentage of patients in each category (0–5, 6–9, and >9) will be presented.
- Normalized brain volume at baseline: summary statistics calculated will include mean, median, SD, minimum, and maximum
- Number of T1 hypo intense lesion (black holes) count at baseline: summary statistics calculated will include mean, median, SD, minimum, and maximum

Past MRI Data (recorded at Screening):

- Number of previous Gd-enhancing T1 lesions: the number and percentage of patients in each category (i.e., 0, 1, >1 , and not evaluable)
- Number of previous T2 lesions: the number and percentage of patients in each category (0–5, 6–9, and >9)

4.3.7 OLE Baseline

Demography and baseline characteristics analysis will be repeated and updated for the OLE period.

EDSS at OLE baseline is defined as the latest EDSS score prior to or on the start of the OLE period.

For all other analysis, OLE Baseline score is the latest score prior to or on the OLE first dose, collected at Week 96 and/or OLE Week 0, unless specified specifically. Patients who have none of these scores available will be excluded from the analyses requiring OLE baseline score.

4.4 EFFICACY ANALYSIS

All statistical hypotheses for the primary and secondary endpoints and treatment comparisons will be tested at the 5% significance level ($\alpha=0.05$) against two-sided alternatives.

For all assessments, the baseline value will be used as the last non-missing value on or before the date of the first infusion of study medication. See Section 4.3.2 for baseline EDSS and Section 4.4.2.4 for time-to-confirmed sustained disability progression.

All primary and secondary efficacy endpoints will be analyzed stratified by geographical region (United States vs. ROW) and baseline EDSS (<4.0 vs. ≥ 4.0).

For all analyses during OLE and combined periods of double-blind and OLE, a pooled efficacy analysis of WA21092 and WA21093 will be performed.

4.4.1 Primary Efficacy Endpoint, Annualized Protocol-Defined Relapse Rate by 2 Years (96 weeks)

Significance Level

The null hypothesis will be tested at the $\alpha=0.05$ level (two-sided test).

- H_0 (null hypothesis): there is no statistically significant difference between the ocrelizumab group and interferon beta-1a 44 μg SC group in the annualized protocol-defined relapse rate at 2 years.
- H_1 (alternative hypothesis): there is a statistically significant difference between the ocrelizumab group and interferon beta-1a 44 μg SC group in the annualized protocol-defined relapse rate at 2 years.

Annualized protocol-defined relapse rate at 2 years between the ocrelizumab dose groups and interferon beta-1a 44 μg SC group will be compared using the negative binomial model, adjusting for geographical region (United States vs. ROW) and baseline EDSS score (<4.0 vs. ≥ 4.0). If the test result for comparing the 600-mg ocrelizumab group and the interferon beta-1a 44 μg SC group is statistically significant at $\alpha < 0.05$ level (two-sided test), it will be concluded that the 600-mg ocrelizumab group demonstrated a superior effect of reducing the annualized protocol-defined relapse rate when compared with the interferon beta-1a 44 μg SC group.

Protocol-Defined Relapse

A protocol-defined relapse is defined as the occurrence of new or worsening neurological symptoms attributable to MS and immediately preceded by a relatively stable or improving neurological state of least 30 days. Symptoms must persist for >24 hours and should not be attributable to confounding clinical factors (e.g., fever, infection, injury, or adverse reactions to concomitant medications). The new or worsening neurological symptoms must be accompanied by objective neurological worsening consistent with an increase of at least half a step on the EDSS score, or 2 points on one of the appropriate FSS, or 1 point on two or more of the appropriate FSS. The change must affect the selected FSS (i.e., Pyramidal, Gait, Cerebellar, Brainstem, Sensory, or Visual). Episodic spasms, sexual dysfunction, fatigue, mood change, or bladder or bowel urgency or incontinence will not suffice to establish the diagnosis of a relapse.

Information related to a protocol-defined relapse will be captured on a clinical relapse event case report form (CRF) page. If the following criteria are satisfied, the clinical relapse will qualify as a protocol-defined relapse:

- Check-box of “Did symptoms persist for >24 hours and were not being attributable...” on the Clinical MS relapse event is checked.
- EDSS scores from a visit occurring on or after the onset date of relapse needs to be at least half a step from the previous EDSS score; OR for FSS domains involved in

the relapse event (indicated on the Clinical MS Relapse page), an increase of at least 2 points on one appropriate FSS domain or at least 1 point on two or more appropriate FSS domains.

- There is no protocol-defined relapse within 30 days before the start date of the clinical relapse.

Protocol defined relapse will be derived following the steps below:

1. Clinical relapse is reported on eCRF.
2. “Did symptoms persist for >24 hours and were not being attributable...” is checked ‘Yes’ on the Clinical MS relapse event form.
3. Check if the first EDSS assessment at a visit (unscheduled or scheduled) on or after the onset date of the relapse is increased by ≥ 0.5 steps from the previous EDSS; OR SELECTED FSS domains relevant to the relapse event (pyramidal, ambulation, cerebellar, brainstem, sensory, or converted visual) are increased by ≥ 2 points on one domain or ≥ 1 point on two or more domains. When deriving this step do the following:
 - Take the last EDSS/FSS score before each clinical relapse onset date
 - Take the first EDSS/FSS score on or after each clinical relapse onset date
 - Calculate the difference between the two scores
 - Select clinical relapses where there is an increase of ≥ 0.5 in EDSS OR ≥ 2 on one appropriate FSS domain OR ≥ 1 on two or more appropriate FSS domains
4. For each relapse that satisfies the 3 criteria above, check if the following relapses are within 30 days (i.e., the onset dates are ≤ 30 days apart). If they are within 30 days, then the later relapses are not protocol-defined relapses.

Analysis Methods

The ITT Population analysis will be presented.

The total number of protocol-defined relapses for each patient will be counted. The exposure time will be calculated as follows:

$$\text{Exposure Time} = (\text{Early treatment discontinued date or date of Week 96 visit}) - \text{date of study Day 1} + 1 / 365.25$$

All available data during the 96-week treatment period will be used for the analysis. For patients who discontinue the treatment early, only data that are collected before the early treatment discontinuation will be used in this analysis (with the exception of subsequent data used to confirm disability progression post-discontinuation of study treatment).

The annualized protocol-defined relapse rate at Week 96 will be analyzed using a negative binomial model, fitted in SAS using the GENMOD procedure. The model will include, for each patient, the total number of protocol-defined relapses with onset between randomization date and early treatment discontinued date/date of Week 96 as response variable and treatment group, baseline EDSS score (< 4.0 vs. ≥ 4.0), and

geographical region (United States vs. ROW) as covariates. In order to account for different study treatment exposure durations among patients, log-transformed exposure time will be included in the model as an “offset” variable for appropriate computation of relapse rate. The rate ratio and the associated two-sided 95% confidence interval will be provided to compare the ocrelizumab and interferon beta-1a 44 µg SC groups. The estimated relapse rate and its two-sided 95% confidence intervals will be provided for each treatment group.

Sample SAS code can be found below (SAS code is regarded as “draft” until fully validated at the analysis stage):

```
proc genmod data=ARR;
  class ARMCD REGION BEDSSCAT;
  model N_PDR = ARMCD REGION BEDSSCAT / offset=EXPLOG link=log
dist=negbin type=3;
  lsmeans ARMCD / exp cl;
  ods output lsmeans=lsm;
  ods output ParameterEstimates=est;
run;
```

The unadjusted annualized protocol-defined relapse rate at Week 96 will also be presented for each treatment group. This is defined for each treatment group as the total number of protocol-defined relapses for all patients in the treatment group, divided by the total number of patient-years of exposure to that study treatment.

Sensitivity and Robustness Checks

The primary analysis described above will be repeated for the per-protocol population as a sensitivity analysis.

The primary analysis described above will be repeated for the ITT population but will exclude patients who received no study medication, as a sensitivity analysis.

As a sensitivity analysis, the primary analysis negative binomial model described above will be adjusted by the following additional covariates: number of relapses occurring within the 2 years prior to study entry, baseline presence of Gd lesions (present or absent), prior MS treatment, and age (<40, ≥40).

A Poisson model with the same covariates as the primary analysis negative binomial model will be fitted.

Three further sensitivity analyses will be undertaken:

- The annualized protocol-defined relapse rate at Week 96 will be calculated including all protocol-defined relapses occurring during the 96-week, double-blind, double-dummy phase or the SFU Phase, up to 96 weeks after randomization. In this analysis, the exposure time will be calculated as follows:

$$\text{Exposure Time} = ((\text{Date of Week 96 visit or date of last visit up to 96 weeks after randomization}) - \text{date of study Day 1} + 1) / 365.25$$

- A sensitivity analysis for the annualized protocol-defined relapse rate at Week 96 using multiple imputations will be performed to explore the potential influence of informative dropouts on the results of the primary efficacy analyses. The multiple imputations will be used to impute the events for patients who discontinued treatment early during the 96-week, double-blind, double-dummy phase without any protocol-defined relapse during the 30 days prior to discontinuation of study treatment. Multiple imputation inference involves three distinct phases:
 1. The missing data are filled in “m” times to generate “m” complete data sets. Instead of filling in a single value for each missing value, multiple imputation replaces each missing value with a set of “m” plausible values that represent the uncertainty about the right value to impute.
 2. The “m” complete data sets are analyzed using standard statistical analyses.
 3. The results from the “m” complete data sets are combined to produce inferential results.

In this analysis, 50% of the patients who discontinued treatment early during the 96-week, double-blind, double-dummy phase without any protocol-defined relapse during the 30 days prior to discontinuation of study treatment will be randomly assigned to have an event at the date of treatment discontinuation; the other 50% of these patients will be censored at the date of treatment discontinuation. A total of 1000 (m = 1000) imputed datasets will be produced.

The primary model described in the “Analysis Methods” section above will be applied to each of the imputed datasets. Each imputed dataset will produce an estimate of the difference between ocrelizumab and interferon beta-1a 44 µg SC. The multiple imputation estimator of the difference between ocrelizumab and interferon beta-1a 44 µg SC is the average of the individual 1000 estimators. The variance of the estimator is the combination of the between- and within-imputation variability ([Carpenter and Kenward 2007](#)).

- The annualized protocol-defined relapse rate at Week 96 will be calculated such that patients who discontinued treatment early during the 96-week, double-blind, double-dummy phase without any protocol-defined relapse during the 30 days prior to discontinuation of study treatment will be counted as having had a relapse on the date of treatment discontinuation. This approach is similar to above, but here the described approach is applied to 100% of such patients (hence no imputation), rather than randomly to 50% of such patients (with multiple imputation).

OLE Phase

The annualized protocol-defined relapse rate as defined above will be calculated for every year from Study Day 1 and from the start of the OLE period (Year 3).

Each yearly interval will be defined as the follows,

- Year 1: Treatment start date up to -1 day before Week 48; if WEEK 48 is missing then take the minimum of treatment start date+48*7 or treatment end date as the last day
- Year 2 (only exists if treatment end date is strictly after the last day of Year 1): Year 1 end date+1 up to either OLE start date if it is available, or the treatment end date
- Year 3 (only exists if OLE start date is not missing and OLE end date is strictly after the last day of Year 2): Year 2 end date+1 up to 1 day before OLE Week 48; if OLE Week 48 is missing then take the minimum of (OLE start date+48*7 or OLE end date or last known alive date as the last day).
- Year 4: Similar to Year 3 but from OLE Week 48+1 up to 1 day before OLE Week 96.
- The subsequent years will be similar to Year 4 definition with addition of 48 weeks for yearly interval.

So, ARR will be calculated and presented at every 48 weeks interval.

A GEE Poisson model will be performed, with repeated measurements for each patient, the yearly total number of protocol-defined relapses as response variable and treatment group, baseline EDSS score (< 4.0 vs. ≥ 4.0), geographical region (United States vs. ROW), year number, and the interaction between treatment group and year number as covariates.

Summary table should contain;

- ARR for each treatment arm and rate ratio within each year
- Rate ratio between consecutive years for each treatment arm
- Rate ratio between Year 1 ocrelizumab arm and OLE Year 1 (i.e., Year 3) interferon beta-1a44 µg SC arm and corresponding p-value
- Rate ratio between Year 2 ocrelizumab arm and OLE Year 2 (i.e., Year 4) interferon beta-1a44 µg SC arm and corresponding p-value

p-values will be reported for rate ratio within each year and between consecutive years for comparison between treatments.

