8.2.1 Primary Efficacy Analysis

The primary efficacy analysis for this trial will compare annualized protocol-defined relapse rate by 96 weeks between ocrelizumab group and Rebif group. The annualized relapse rates by 96 weeks will be analyzed with use of a negative binomial model, adjusting for region (United States vs. ROW) and baseline EDSS (<4.0 vs. ≥4.0). The adjusted ARR and the 2-sided 95% CIs for the relapse rates will be presented along with the p-value.

Other sensitivity analyses may also be performed for the primary efficacy endpoint (and documented in the SAP).

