2.3 DETERMINATION OF SAMPLE SIZE

The sample size for this study was estimated on the basis of data from previous RRMS trials, with use of two-sided tests with an experiment-wise alpha of 0.05. The ARR at 96 weeks in patients receiving ocrelizumab is predicted to be 0.165 (SD of approximately 0.60), compared with 0.33 (SD of approximately 0.80) in patients receiving the control treatment (interferon beta-1a 44 µg SC); this represents a relative reduction of approximately 50% with ocrelizumab treatment compared with the active comparator. For the ARR, a t-test was used to determine the sample size between ocrelizumab and interferon beta-1a 44 µg SC. The sample size of 400 patients per treatment group provides 84% power, maintaining the type I error rate of 0.05 and with the assumption of a dropout rate of approximately 20% (with the assumption that relative reduction among patient dropout is 25%).

For confirmed disability progression, a two group test of equal exponential survival with exponential dropout was used to determine the sample size. Assuming the 2-year confirmed disability progression rate is 18% for the interferon beta-1a 44 µg SC arm and 12.6% for the ocrelizumab arm (this represents a relative reduction of 30% on ocrelizumab compared to the active comparator), and assuming a dropout rate of 20% over 2 years approximately, the sample size of 400 per arm will provide 80% power,

maintaining the type I error rate of 0.05 based on the pooled analysis of two RMS studies (800 patients treated with ocrelizumab 600 mg and 800 patients treated with interferon beta-1a 44 µg SC).

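### The primary ARR model has no baseline measure of relapse activity, although two candidates are collected; this is an efficiency choice of uncertain size, not an error

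*SAP*

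**What the plan says.** SAP 4.4.1 fits relapse counts by negative binomial regression with a log-exposure offset. The terms are treatment, EDSS category (below 4.0, or 4.0 and above) and "geographical region (United States vs. ROW) as covariates". Protocol 8.2.1 specifies the same model, "adjusting for region (United States vs. ROW) and baseline EDSS" category. These two factors are the randomization strata (SAP 3.1), and SAP 4.4 applies them to every primary and secondary endpoint.

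A sensitivity model in SAP 4.4.1 adds four covariates: "number of relapses occurring within the 2 years prior to study entry, baseline presence of Gd lesions (present or absent", plus prior MS treatment and age group. Relapses in the past 2 years are tabulated at baseline under SAP 4.3.2, and baseline Gd-enhancing lesions under SAP 4.3.6.

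The count and continuous secondary models each carry a baseline measure of their outcome:

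- T1 Gd lesions: baseline Gd status (SAP 4.4.2.4)
- T2 lesions: baseline T2 count (4.4.2.5)
- Black holes: baseline T1-hypointense count (4.4.2.8)
- MSFC: baseline MSFC (4.4.2.9)
- Brain volume: Week 24 volume, the reference point for that endpoint (4.4.2.10)
- SF-36 PCS: baseline PCS (4.4.2.11)

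The sample size did not use covariates: "For the ARR, a t-test was used to determine the sample size between ocrelizumab and interferon beta-1a 44 µg SC" (SAP 2.3).

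**The concern.** Relapse history is the obvious baseline counterpart of on-study relapse rate. Protocol 5.10.3 also says that Gd-enhancing lesions have been linked to relapses. Both variables are already in hand, and the SAP considers them relevant enough for a sensitivity model. If they are prognostic, placing them in the primary model would narrow the interval for the rate ratio and reduce the influence of chance imbalance. The rate ratio under a log link is collapsible, so the quantity being estimated would not change. At stake is precision on the endpoint that gates the testing hierarchy. Validity is not in question.

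**Working it through.** **Inputs (SAP 2.3).** Control ARR 0.33, SD 0.80; ocrelizumab ARR 0.165, SD 0.60; 400 per arm; two-sided 0.05; 20% dropout, with a relative reduction of 25% among dropouts.

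**1. The plan's own power.** The blended reduction is 0.8 × 50% + 0.2 × 25% = 45%, so the difference is 0.33 × 0.45 = 0.1485. The common SD is √[(0.60² + 0.80²)/2] = 0.707. A two-sample test with 400 per arm gives 84.4%, which matches "The sample size of 400 patients per treatment group provides 84% power". A 50% reduction with 320 completers per arm gives 83.9%. No covariate is needed on either route.

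**2. Dispersion implied by the planning SDs.** Follow-up is 96 × 7/365.25 = 1.840 years, mean count μ = ARR × 1.840, and k = [(SD × 1.840)² − μ]/μ².

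- Control: μ = 0.607, k = (2.166 − 0.607)/0.369 = 4.23.
- Ocrelizumab at 0.165: μ = 0.304, k = 9.93.
- Ocrelizumab at the diluted rate 0.33 × 0.55 = 0.1815: μ = 0.334, k = 7.93.

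**3. Effect of adjustment.** Let the covariates remove a fraction f of k. Then Var(log RR) = Σ over arms of [1/μ + k(1 − f)]/400, the extra-patient equivalent is Var(f = 0)/Var(f) − 1, and power is Φ(|ln 0.55|/SE − 1.96). The values of f, and k = 1, 2 and 3, are assumptions. The ocrelizumab rate is 0.1815 throughout, to match the ratio of 0.55.

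| k (control / ocrelizumab) | f | Extra patients | Power |
|---|---|---|---|
| 4.23 / 7.93 | 0 | none | 83.1% |
| 4.23 / 7.93 | 5% | 3.8% | 84.4% |
| 4.23 / 7.93 | 10% | 7.8% | 85.7% |
| 4.23 / 7.93 | 20% | 16.9% | 88.4% |
| 1 / 1 | 0 → 10% | 3.1% | 99.6% → 99.7% |
| 2 / 2 | 0 → 10% | 4.9% | 98.2% → 98.6% |
| 3 / 3 | 0 → 10% | 6.0% | 95.6% → 96.5% |

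Keeping k = 9.93 for ocrelizumab instead gives a starting power of 78.7% and extra-patient equivalents of 3.9% to 17.7%. At f = 0 the gain is nil.

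**4. Dependence on the meaning of share.** Suppose the share s is instead the part of the squared coefficient of variation of patients' underlying rates that the covariates explain. Residual dispersion is then (1 + k)/(1 + sk) − 1, and the gain is larger. With average exposure at 90% of 96 weeks and s = 10%, the variance of log RR falls 5% at k = 1, 11% at k = 2 and 22% at k = 4. Power moves from 99.4% to 99.6%, 97.7% to 98.7% and 90.9% to 96.1%.

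**5. Simulation (about 500 trials per setting, true RR 0.70, k = 1).** With assumed rate ratios of 1.16 per prior relapse and 1.22 for Gd, the mean SE goes from 0.128 to 0.127. With 1.35 and 1.49 it goes from 0.127 to 0.124, equivalent to (0.127/0.124)² − 1 = 4.9% more patients. The mean rate ratio was about 0.70 with and without the covariates. Across the settings run (k = 1 and 2), rejection at RR = 1 was 4% to 7% for both models (simulation error about 1 point).

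**6. Missing Gd.** Protocol 5.3 admits patients who cannot receive Gd, and the SAP has no rule for a missing Gd covariate. With complete-case fitting, the weaker effects and 5% missing, the SE rises from 0.127 to 0.130. On the planning t-test scale, a covariate R² of 5% with 5% missing returns power to 84.4%. A not-available level keeps all randomized patients in the model.

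**The case against.** The case for leaving the model alone has real weight. Adjusting for exactly the randomization strata is a coherent rule, and the sensitivity model already reports a covariate-adjusted rate ratio. No bias, type I error problem or contradiction follows. All of that stands, and it makes this an efficiency preference.

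The size of the gain is also open to challenge. The documents give no prognostic strength for either covariate; Protocol 5.10.3 is qualitative and concerns Gd, not relapse count. Protocol 5.2 requires recent attacks, which narrows the spread of the count. The dispersions of 4.23 and 7.93 to 9.93 are back-calculated from approximate SDs as if everyone had full follow-up, whereas the planned model fits a single dispersion. At moderate dispersion, power is already above 95%. This also stands, so the gain can only be given as a range that includes nil.

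The objection that missing Gd status would cost patients does not stand once a not-available category is specified.

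A reader might infer that the plan gives up precision for free, or that the trial was underpowered. The documents support neither. The gain is unquantified and needs a missing-data rule, and the promised 84% is reached without it. Pairing a ratio of 0.55 with the undiluted 0.165 rate in the variance gives a starting power of 78%; the consistent figure is 79% to 83%, and only at the extreme implied dispersions.

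**Conclusion.** The point holds as a modest, low-cost improvement to the plan. ARR is the one count or continuous endpoint in the primary and secondary set without a baseline measure of its own outcome, and suitable covariates are collected. The omission is not an error.

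If 5% to 20% of the dispersion implied by the planning SDs is removed, the gain is worth about 4% to 17% more patients. At dispersion 1 to 3, removing 10% is worth about 3% to 6% more patients and at most about 1 point of power. Defining the share by the squared coefficient of variation gives more, and weak covariates give almost nothing. These figures rest on assumed shares and a rate ratio of 0.55.

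A reader might also conclude that the primary model should now be replaced. SAP 2.4 lists the primary report as completed, with a 12 May 2015 cutoff for this study, and the current SAP text postdates unblinding. Replacing the model would be a post hoc change to a reported confirmatory analysis.

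**What to change.** Prospectively, for a relapse-rate trial of this kind: pre-specify in the primary negative binomial model the number of relapses in the 2 years before entry and baseline Gd status as present, absent or not available, so that no ITT patient is dropped. State how the relapse count is coded. Report the strata-only model as an additional sensitivity analysis beside the existing four-covariate model. This is not a simple exchange of the two current models, because the existing sensitivity model also contains prior MS treatment and age.

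For this trial: leave the reported confirmatory model in place, add a missing-Gd rule to the sensitivity model in SAP 4.4.1, and present its result beside the primary one. The yearly GEE Poisson model for the extension, which also adjusts only for the strata, could carry the same covariates, labelled exploratory, in the final report that SAP 2.4 still lists as planned.

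The cost is one missing-category rule, a slightly larger model and wording in the analysis plan. No new data are needed.
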